9. The individual structured feedback for all scanning modalities collected at teaching seminar 2 and 3.
10. Access to Pre/post self-quizzes before and after each training seminar and access to the results.

Participants will receive a notification by email or on their phones, when there is activity on the online platform. The overall purpose of this online platform is to support the participant in the continuous learning process. We aim to create awareness about the learning process, individual focus points and goals, the importance of training and gaining experience, and to make guidance available when difficulties/problems are encountered.

Teaching seminars (day 7, 30 and 90)

The educational intervention includes three teaching seminars on days 7, 30 and 90. All seminar days have a similar overall structure with a focus on hands-on training and the individual participant's development of scanning competences. However, the teaching aims are different on each seminar which means different focus in the teaching and different activities between seminar days.

[figure not shown]
Teaching seminar 1

The aim of the first teaching seminar is to give participants first-hand experiences with performing POCUS scans and to create a foundation of knowledge and experience which is to be further developed in the coming months. Furthermore, the participants will learn to perform five of the POCUS scans in the selected curriculum.

The teaching seminar will start off with a short lecture summarizing the theoretical foundation for using POCUS and the participants preparation. The teachers will summarize the results of the first assignment and address questions, barriers and concerns raised by participants. Afterwards, a short lecture will follow introducing basic transducer manipulation and image optimization. The participants are then introduced to the five selected POCUS modalities in a short lecture summarizing the fundamentals of the five scans. The participants are then divided into small groups of four participants based on their POCUS experience as declared in the prior assignment. Participants working in the same practice, will be separated into different group to ensure a good

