This phase in the learning process is considered and articulated as a developing phase, where participants continue to develop their scanning skills and routines. The participants are encouraged to use POCUS examinations on all patients with relevant clinical conditions suited for POCUS and to work with the integration of POCUS into their clinical practice and medical decision making. It is important in this phase that the participants develop routines and become comfortable performing POCUS examinations. During the eight weeks between the teaching seminars 2 and 3, participants are encouraged to register all POCUS examinations in their individual logbook in the online platform and note reflections and questions that occur during this process. The participants will still have the opportunity to consult the teachers during this phase by uploading questions, images or videos to the online platform. It is again recommended that participants perform a minimum of three POCUS examinations on patients within each scanning modalities during the eight weeks and that participants upload at least one POCUS examination of each of the five new scanning modalities for review and feed-back (assignments 8-12).

During the eight weeks, participants will be invited to participate in two half-an-hour webinars (on day 50 and 75). At these webinars, one of the teachers will go through some of the encountered problems and difficulties uploaded or posted on the online platform and present images and videos of common pathologies with the 10 selected POCUS modalities. Participants will also have the opportunity to ask questions and the teacher will have an ultrasound device and a volunteer available for live POCUS demonstration.

Before the third and final teaching seminar, the participants will be asked to complete a pre-self-quiz and to send in a list of questions or topics that they want included in the final teaching seminar (assignment 13).

[figure not shown]
Teaching seminar 3

Before the final teaching seminar, the teachers will prepare feedback for each participant based on the information gathered about each participant, i.e., from notes in the logbook, the uploaded scans, impressions from teaching seminars, the correspondence in the chat function, etc.

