The structure of this final teaching seminar is similar to previous seminars. However, besides validating, adjusting and improving the participants' POCUS examinations, the goal is also to evaluate the participants' learning process, scanning competence and to offer guidance for future development.

Like the second seminar, this teaching seminar starts off with a plenum session where encountered experiences, problems or difficulties are shared and discussed. The teachers will address questions raised on the online platform and common difficulties identifies in the uploaded scans. The participants are invited to openly share and discuss. Afterwards, the participants are divided into small groups of 4 participants and they then circulate between hands-on workshop stations, as they did on the previous seminars. At the workshop stations, the participants will take turns demonstrating the POCUS scan for the teacher (figure 5). The teacher will then assess the participants' individual scanning competences using item 2-5 on the OSAUS score, give feedback on ways to improve performance and help the participants to set new learning goals and focus points for the continuous learning process. The participants will also receive suggestions for improvement from fellow participants, as the instructor invites to a discussion about the use of the scanning modality in general practice. The feedbacks and teacher suggestions are uploaded to the online platform, so participants may consult these at a later stage.

Figure 5. Structure of hands-on workshops on the third teaching seminar

At the end of the teaching seminar, participants will be asked to evaluate the educational intervention, their own learning outcome and to identify unanswered questions in the small groups. Afterwards, these are discussed in a final plenary session for all participants and teachers.

If needed, the teachers will upload additional information to the online platform to support the participants' further learning.

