After the teaching seminar a final post-self-test is available (a replication of the pre-self-test for teaching seminar 3) for the participants to create awareness about continuous learning process and to illustrate to what extent the learning objectives of the teaching seminar have been reached. The teachers will reach out to participants, where the test scores reveal problems or difficulties, as well as participants, where the demonstration of the scan revealed specific difficulties. These participants will be offered additional support.

Competence assessment by experts

On the third teaching seminar, participants will have their scanning competence assessed by external experts. These experts are blinded to the participants previous experience and learning process. During the workshop rotation, each participant will step-a-side to have their competence assessed by a POCUS expert. This assessment will be staggered from the scanning modality being the topic of the workshop. Hence, the participants will first have the workshop with a specific scanning modality and then immediately after, during the next workshop, they will take turns, stepping-a-side for 10 minutes to have their scanning competence for the modality assessed.

The experts will assess the participants by asking the following questions:

- In which clinical scenarios would you perform this POCUS examination (Item 1 in the OSAUS)

The experts will ask participants to demonstrate the POCUS examination (for maximum five minutes) to assess the following:

- Applied knowledge of the ultrasound equipment (Item 2 in the OSAUS)
- Image optimisation (Item 3 in the OSAUS)
- Systematic examination (Item 4 in the OSAUS)
- Interpretation of images (Item 5 in the OSAUS)

The experts will present the participants with two picture of common pathology and ask the participants the following questions:

- How would you interpret these ultrasound findings? (Item 5 in the OSAUS)
- If you were to describe this examination in the medical record, what would you write? (Item 6 in the OSAUS)
- What would you do if you found it? (Item 7 in the OSAUS)

Immediately before each competence assessment by experts, participants will be asked to fill out a questionnaire where they declare whether or not they have POCUS scanning competence within this scanning modality to perform the scan un-supervised in general practice. The expert assessor are blinded to this declaration.

[figure not shown]
Participant commitment

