(S5): We calculate the proportion of GPs, who rate themselves as competent to perform POCUS un-supervised in general practice, after six months, within each of the ten scanning modalities.

Implementation process-related outcomes

(PR1): The GPs keep a log book of all scans they perform. The number of scans of the 10 modalities performed during months 1 to 3 and month 4 to 6 are summarized. Results are presented as the mean number of performed POCUS examinations by each GP during months 1 to 3 and during months 4 to 6.

(PR2): The number of adverse events and near-miss cases associated with the use of POCUS during months 1 to 6 will be summarized for each of the ten scanning modalities. Results will be presented as total numbers and frequencies.

(PR3): We will graphically evaluate the mean OSAUS score (y-axis) at the end of the educational intervention (3 months after baseline) as a function of each of the following educational aspects (x-axis).

- a. course days
- b. webinars,
- c. pre-and post-self-quizzes
- d. assignments (upload and feed-back)
- e. scans performed during the educational intervention

Background characteristics of participating GPs

At baseline the following participant characteristics will be collected: Age (years), gender (M, F, other), year of graduation from medical school, experience as a GP working in general practice (years), previous experience with ultrasound use (yes/no), previous training in ultrasound use (yes/no), scanner type (low range, mid range, high end), type of employment (practice owner/ employed/other), type of practice (collaboration, partnership, solo), location of practice (urban, rural, mixed), distance to nearest radiology department (km), number of patients assigned to the practice, number of GPs working in the practice will be presented.

13 Time schedule

Figure 7 Study timeline

Week	8	9	10	11	12	13	14	15	16	17	18	19	20	21	22	23	24	25	26	27	28	29	30	31	32	33	34	35
webinar																												
Teaching seminar																												
Skills assessment																												
Educational period																												
Transition period																												

Teaching seminars: Marts 3rd and 30th and June 9th 2022

Skills assessment: June 9th and September 1st 2022

Data collection educational period (months 1-3): Marts 3rd – June 9th 2022

Data collection after educational intervention (months 4-6): June 10th – September 1st 2022

14 Sample size

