During the study, the principal investigator is available for consultation for the participating GPs in order to resolve any problems or obstacles. Monthly reminders will be sent to the participating GPs remaining them to include patients and contact the research team in case of problems.

19 Data management

The OSAUS assessment will be filled out by the expert assessors in questionnaires using tablets. The expert assessors will access the SurveyXact app (Rambøll, Aarhus, Denmark) on the tablets using unique access links. The Raters will then insert the GP ID number and fill out the questionnaire. After filling out the questionnaire, the access will close. As internet access may be unstable at the training facilities, the questionnaire can be filled out on both offline and online tablets. If the tablet is online, the questionnaire is stored directly on SurveyXact's server. If the tablet is offline, the questionnaire is stored safely in the app for direct upload when internet access is achieved. Questionnaires stored in the app cannot be accessed. The questionnaires stored on SurveyXact's server can only be accessed by the research team. Backup copies from the SurveyXact server are weekly collected and stored at a secure server at Aalborg University during the data collection period.

The participating GPs will be asked to bring paper versions of the registration sheets (Logbook) at the third training day and the final day of skills assessment, where the principal investigator will collect these and bring them to CAM AAU, where the questionnaires will be imputed into the database by a research assistant.

All study data registered on the online platform will be transferred and imputed in an excel sheet at the end of the educational intervention. All digital study related data are stored on secure server on Aalborg University and handled according to the General Data Protection Regulation.

20a Statistical methods for analysing primary and secondary outcomes.

All statistical analyses will be performed using STATA version 17 (StataCorp, Texas, USA) and analyzed according to a predefined statistical analysis plan, which will be uploaded prior to the data collection for the primary outcome (three months after baseline).

20b Methods for any additional analyses (e.g. subgroup and adjusted analyses).

Sensitivity analyses will be performed without imputation of missing values by only including complete OSAUS scores.

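### Does scoring at three months straight after a coached workshop, with no such workshop scheduled at six months, spoil the retention comparison?

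*Protocol*

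**What the plan says.** Protocol 11a (Teaching seminar 3) has a teacher watch each GP scan and rate "individual scanning competences using item 2-5 on the OSAUS score, give feedback on ways to improve performance"; fellow participants add suggestions. Under Competence assessment by experts, "the participants will first have the workshop with a specific scanning modality and then immediately after, during the next workshop, they will take turns" stepping aside for a blinded expert, who scores all seven items for the modality just practised. The self-rating behind S4 comes at the same moment: "Immediately before each competence assessment by experts, participants will be asked to fill out a questionnaire".

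The timetable lists no teaching at six months:

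- Protocol 11a: "The educational intervention includes three teaching seminars on days 7, 30 and 90". The third is described as the last: "Before the third and final teaching seminar, the participants will be asked to complete a pre-self-quiz".
- Protocol 13: "Teaching seminars: Marts 3rd and 30th and June 9th 2022", but "Skills assessment: June 9th and September 1st 2022". June is both a teaching and an assessment day; September is an assessment day only. SAP 1 gives 7 and 8 September for the second assessment and also mentions no teaching there.
- Protocol 19 collects logbooks "at the third training day and the final day of skills assessment", which sets the training day apart from the last assessment.

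SAP 7 sets out one rating procedure for both visits: the assessors, their blinding, the questions, the scanning time limit and the pathology picture. It does not say what the GP does beforehand in September. SAP 5.3 defines S6 as the change from three to six months, tested with a paired t-test.

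**The concern.** Items 2-5 are coached and then scored by the expert in the next rotation slot. Part of the three-month score may therefore be a short-lived effect of having just been corrected on that scan. If September has no such lead-in, that part disappears by the second visit and shows up as a fall.

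The study has one arm, so no control group can separate a fading same-day gain from loss of competence. Assessor blinding does not help either, because the GP's performance on the day really is better. Maintenance is half of the overarching aim in Protocol 7, and SAP 10 calls p < 0.05 significant. The risk is that a significant S6 fall is read as a failure to retain skills when some of it reflects the conditions of the first measurement.

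**Working it through.** **Reproducing the plan's figures.** Protocol 14 and SAP 8: 20 × 0.80 = 16 GPs; 16 × 10 modalities = 160 questionnaires per time point. Both agree. The plan has no power or precision calculation to reproduce.

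**Inputs.** n = 16 (Protocol 14). Each modality has a maximum of 35 points, and the primary score is a percentage of maximum over ten modalities (Protocol 12, SAP 5.1). Significance is at 0.05 (SAP 10), taken as two-sided. The documents give no coaching gain, SD or correlation between visits. The following are therefore assumptions: a lift of g points on each of items 2-5 in every modality and GP, between-GP SD of 5 to 15 percentage points, and within-GP correlation r of 0.8 or 0.5.

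**Lift in the three-month score.** 100 × (4 items × g × 10) / (35 × 10) = 400g/35.

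- g = 0.25: 100/35 = 2.86 points
- g = 0.5: 200/35 = 5.71 points
- g = 1: 400/35 = 11.43 points

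Only the part that has faded by September enters S6.

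**Precision of S6.** SD of the difference = SD × √(2(1 − r)). Half-width = t(0.975, 15) × SD of the difference / √16, with t = 2.131. The last column is the fully transient lift per item that equals the half-width: half-width × 35/400.

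| SD | r | SD of difference | Half-width | Lift per item |
|---|---|---|---|---|
| 5 | 0.8 | 3.16 | 1.69 | 0.15 |
| 5 | 0.5 | 5.00 | 2.66 | 0.23 |
| 10 | 0.8 | 6.32 | 3.37 | 0.29 |
| 10 | 0.5 | 10.00 | 5.33 | 0.47 |
| 15 | 0.8 | 9.49 | 5.06 | 0.44 |
| 15 | 0.5 | 15.00 | 7.99 | 0.70 |

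**Chance of a significant fall with no lasting loss** (noncentral t, 15 df, lift fully transient, SD 10). With g = 0.25 it is about 39% (r = 0.8) to 19% (r = 0.5). With g = 0.5 it is about 92% to 57%. The half-width is therefore no safety margin: a lift of 2.86 points lies inside the 3.37-point half-width and still gives a significant fall in about 39% of studies, because bias adds to sampling error.

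**Which comparisons are affected.** P1 and P2 are summarised separately in Protocol 12 and SAP 5.1. Neither document plans a test of P2 against P1, S3 against S2 or S5 against S4. S6 is the only planned contrast between the visits, and SAP 5.3 lists it as an additional outcome not predefined in the protocol.

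**What S6 is meant to measure.** Protocol 7 asks for competence at the end of the programme and whether it holds three months later; Protocol 6 gives decay of skills as the motive. 9 June to 1 September is 84 days, and to 7 or 8 September 90 or 91 days. A score at the last seminar followed by one about three months later, with no seminar between, answers that question. Adding a coached workshop in September would match the conditions but would contaminate P2 as a measure of retained skill.

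**The case for a change.** The strongest case for a change is that the order is deliberate, the same four items are coached and then scored, and neither document mentions the different lead-in to the two visits. With plausible assumed values, a same-day effect alone could make S6 significant. Both P1 and P2 are primary and together carry the maintenance aim, and the remedy would be a few sentences in the SAP.

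Much of this stands. The sequence is as described, the timetable supports an uncoached September session, and the SAP does not say what precedes that rating. SAP 7 uses the same stepping-aside wording for both visits, which leaves some doubt about the September format.

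It does not carry through to a change. Loss of freshly trained performance is part of the decay the study wants to observe, and nothing in the documents marks where a passing gain ends and competence begins. The three-month outcomes are defined as end-of-programme scores and their timing is stated openly, so relabelling them would alter no result. No rule in the plan turns an S6 fall into a claim of lost competence. Other influences also bear on S6, some in the opposite direction: GPs keep scanning in months 4 to 6, the written feedback stays on the platform, and the same questions are asked again.

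**Conclusion.** The observation is right, but no change to the plan follows. S6 sets performance straight after a workshop against delayed performance, so a fall may contain a same-day component. That component might be negligible or might exceed the S6 half-width (3.4 to 5.3 points at SD 10, 1.7 to 8.0 over SD 5 to 15). The documents cannot settle which, because the lift, the SD and the correlation are all assumed here. The illustration also applies one lift to every GP and modality and ignores the ceiling of 5 on each item.

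The design is a fair trade-off: scoring at the end of the last seminar and again about three months later measures what the protocol asks. With respect to this one influence, a flat S6 result would be conservative for maintenance. What precedes the September rating is a detail that the authors know and will naturally describe in the methods of the paper, and the reading of a fall belongs in its discussion. Wording in the SAP would change no data, no estimate and no test.

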During the study, the principal investigator is available for consultation for the participating GPs in order to resolve any problems or obstacles. Monthly reminders will be sent to the participating GPs remaining them to include patients and contact the research team in case of problems.

19 Data management

The OSAUS assessment will be filled out by the expert assessors in questionnaires using tablets. The expert assessors will access the SurveyXact app (Rambøll, Aarhus, Denmark) on the tablets using unique access links. The Raters will then insert the GP ID number and fill out the questionnaire. After filling out the questionnaire, the access will close. As internet access may be unstable at the training facilities, the questionnaire can be filled out on both offline and online tablets. If the tablet is online, the questionnaire is stored directly on SurveyXact's server. If the tablet is offline, the questionnaire is stored safely in the app for direct upload when internet access is achieved. Questionnaires stored in the app cannot be accessed. The questionnaires stored on SurveyXact's server can only be accessed by the research team. Backup copies from the SurveyXact server are weekly collected and stored at a secure server at Aalborg University during the data collection period.

The participating GPs will be asked to bring paper versions of the registration sheets (Logbook) at the third training day and the final day of skills assessment, where the principal investigator will collect these and bring them to CAM AAU, where the questionnaires will be imputed into the database by a research assistant.

All study data registered on the online platform will be transferred and imputed in an excel sheet at the end of the educational intervention. All digital study related data are stored on secure server on Aalborg University and handled according to the General Data Protection Regulation.

20a Statistical methods for analysing primary and secondary outcomes.

All statistical analyses will be performed using STATA version 17 (StataCorp, Texas, USA) and analyzed according to a predefined statistical analysis plan, which will be uploaded prior to the data collection for the primary outcome (three months after baseline).

20b Methods for any additional analyses (e.g. subgroup and adjusted analyses).

Sensitivity analyses will be performed without imputation of missing values by only including complete OSAUS scores.

Sub-analyses will be performed to explore the importance of different educational elements in the intervention. These sub-analyses will be defined in the statistical analysis plan.

20c Missing data

A predictive mean matching (pmm) imputation method will be used to fill in missing values by the command “mi impute pmm” in Stata³⁶, for all OSAUS scores after 3 and 6 months.

Predictive mean matching (PMM) is a partially parametric method that matches the missing value to the observed value with the closest predicted mean³⁷.

Data monitoring

21a Data monitoring committee (DMC).

The principal investigator (CAA) will monitor the data collection and contact the project steering committee in case of problems related to data collection or the validity of the collected data. The principal investigator (CAA) will also contact the steering committee in care of participant drop-out.

21b Description of any interim analyses and stopping guidelines, including who will have access to these interim results and make the final decision to terminate the trial

n/a

22 Harms

The participating GPs will be obliged to report any Suspected Unexpected Serious Adverse Reactions (SUSARs), Serious Adverse Events (SAEs) and Adverse Events (AEs) related or possibly related to the use of POCUS to the adverse event committee.

23 Auditing

n/a

Ethics and dissemination

24 Research ethics approval

The study will be performed in accordance with the Declaration of Helsinki. The project was notified to the regional ethical committee (Den Videnskabsetiske Komité for Region Nordjylland, reference number 2022-000764) who responded that according to Danish Law (komitélovens § 14, stk. 2), no ethical approval is needed for this project.

The project has been registered and conducted according to the regulations of the Danish Data Protection Agency (registration number ID-242-2).

25 Protocol amendments

Any modifications to the protocol that will impact the conduct of the study such as study objectives, study design, patient population, sample sizes, study procedures or significant administrative aspects will be communicated to the Ethics Committee of North Denmark Region for approval. The registration on clinicaltrials.gov will be updated if any of the above-mentioned modifications are made.

26a Consent or assent

Informed consent form the participating GPs will be collected by the principal investigator prior to the study.

26b Additional consent provisions for collection and use of participant data and biological specimens in ancillary studies, if applicable

n/a

27 Confidentiality

Personal information about participants consenting to participate will be stored on a secure server at Aalborg University. All data will be kept for 10 years after completion of the study which in accordance with The European Code of Conduct for Research Integrity.

28 Declaration of interests

The authors declare that they have no competing interests.

29 Access to data

During the educational intervention the following authors will have access to data on the online platform (UM, TMJ, TL, NS, LD, BS, CAA). Participants will during the educational intervention have access to their own data shared on the online platform. The following authors will have access to collected data stored at the secure server at Aalborg University (AR, MBJ and CAA).

30 Ancillary and post-trial care

Any participants who suffer harm from trial participation will be eligible to seek compensation by The Patient Compensation Association.

31a Dissemination policy

We aim to publish positive, negative or inconclusive results of the study in a peer-reviewed journal. The project group will also present results at conferences.

31b Authorship eligibility guidelines

We aim to follow the definition of authors defined on ICMJE's four criteria¹:

- Substantial contributions to the conception or design of the work; or the acquisition, analysis, or interpretation of data for the work; AND
- Drafting the work or revising it critically for important intellectual content; AND
- Final approval of the version to be published; AND
- Agreement to be accountable for all aspects of the work in ensuring that questions related to the accuracy or integrity of any part of the work are appropriately investigated and resolved.

31c Plans for granting public access to the full protocol, participant-level dataset, and statistical code

It is unsure if data can be anonymized sufficiently to be made publicly available.

32 Informed consent materials

The Danish informed consent form will be attached as an appendix

References

¹ International Committee of Medical Journal Editors. Defining the Role of Authors and Contributors. Available from: <http://www.icmje.org/recommendations/browse/roles-and-responsibilities/defining-the-role-of-authors-and-contributors.html>

